3.2 Responsibility for Analyses/In-House Blinding

The statistical analysis of the data obtained from this study will be the responsibility of the Clinical Biostatistics department of the Sponsor.

This study will be conducted as a double-blind study under in-house blinding procedures. The official, final database will not be unblinded until medical/scientific review has been performed, protocol deviations have been identified, and data have been declared final and complete.

The Clinical Biostatistics department will generate the randomized allocation schedule(s) for study intervention assignment. Randomization will be implemented in an IRT.

Blinding issues related to the planned interim analyses are described in Section 3.7.

3.3 HYPOTHESES/ESTIMATION

Objectives of the study are stated in Section 3 of the protocol. This is an estimation study, and no formal hypothesis testing will be performed.

3.4 ANALYSIS ENDPOINTS

Immunogenicity and safety analysis endpoints that will be summarized are listed below.

3.4.1 Immunogenicity Endpoints

A description of immunogenicity assessments is contained in Section 8.2 of the protocol.

Immune responses will be measured for each of the following serotypes contained in V114: 1, 3, 4, 5, 6A, 6B, 7F, 9V, 14, 18C, 19A, 19F, 22F, 23F, and 33F.

The primary immunogenicity analysis endpoints are the anti-PnPs serotype-specific IgG GMCs at 30 days postvaccination with V114 or Prevnar 13TM.

The secondary immunogenicity analysis endpoints include:

- Anti-PnPs serotype-specific OPA GMTs at 30 days postvaccination
- Anti-PnPs serotype-specific GMFR from prevaccination (Day 1) to 30 days postvaccination for both OPA and IgG responses

3.4.2 Safety Endpoints

A description of safety measures is presented in Sections 8.3 and 8.4 of the protocol. The analysis of safety results is described in Section 3.6.2.

Safety and tolerability will be assessed by clinical review of all relevant parameters including AEs and postvaccination temperature measurements following V114 or Prevnar 13TM.

The safety analysis endpoints include:

- Proportion of participants with solicited injection-site AEs (redness/erythema, swelling, tenderness/pain, and hard lump/induration) from Day 1 through Day 14 postvaccination with V114 or Prevnar 13TM
- Proportion of participants with solicited systemic AEs (muscle pain/myalgia, joint pain/arthralgia, headache, and tiredness/fatigue, and hives or welts/urticaria) from Day 1 through Day 14 postvaccination with V114 or Prevnar 13TM
- Proportions of participants with the broad AE categories consisting of any AE, a vaccine-related AE, a SAE, an AE which is both vaccine-related and serious, discontinuation due to an AE, and the proportion of participants who died

- Proportion of participants with maximum temperature measurements meeting the Brighton Collaboration cut points from Day 1 through Day 7 postvaccination with V114 or Prevnar 13™

The timeframe associated with the reporting of AEs is consistent with the collection. Nonserious adverse events (NSAEs) are reported from Day 1 through Day 14 following vaccination. SAEs are reported from Day 1 through completion of study participation.

3.5 ANALYSIS POPULATIONS

3.5.1 Immunogenicity Analysis Populations

The Per-Protocol (PP) population will serve as the primary population for the analysis of immunogenicity data in this study. The PP population consists of all randomized participants without deviations from the protocol that may substantially affect the results of the immunogenicity endpoint. Potential deviations that may result in the exclusion of a participant from the PP population for all immunogenicity analyses include:

- Failure to receive any study vaccine at Visit 1 (Day 1)
- Failure to receive correct clinical material as per randomization schedule
- Receipt of prohibited medication or prohibited vaccine prior to study vaccination

Additional potential deviations that may result in the exclusion of a participant from the PP population for specific immunogenicity analyses (depending on the time point for analysis) include:

- Receipt of prohibited medication or prohibited vaccine prior to a blood sample collection
- Collection of blood sample outside of the pre-specified window (as described in Section 1.3 of the protocol)

The final determination on protocol deviations, and thereby the composition of the PP population, will be made prior to the final unblinding of the database. Participants will be included in the vaccination group to which they are randomized for the analysis of immunogenicity data using the PP population.

A supportive analysis using the Full Analysis Set (FAS) population will also be performed for the primary immunogenicity endpoints. The FAS population consists of all randomized participants who received the study vaccination and have at least 1 serology result at the time point for the analysis. Participants will be included in the vaccination group to which they are randomized for the analysis of immunogenicity data using the FAS population.

3.5.2 Safety Analysis Populations

Safety analyses will be conducted in the All Participants as Treated (APaT) population, which consists of all randomized participants who received at least 1 dose of study

vaccination. Participants will be included in the group corresponding to the study vaccination they actually received for the analysis of safety data using the APaT population. This will be the group to which they are randomized except for participants who take incorrect study vaccination; such participants will be included in the vaccination group corresponding to the study vaccination actually received.

At least 1 temperature measurement obtained subsequent to study intervention is required for inclusion in the analysis of temperature.

3.6 STATISTICAL METHODS

Statistical testing and inference for immunogenicity and safety analyses are described in Section 3.6.1 and Section 3.6.2, respectively. Section 3.6.3 describes how demographic and baseline characteristics will be summarized.

3.6.1 Statistical Methods for Immunogenicity Analyses

This section describes the statistical methods that address the primary and secondary immunogenicity objectives.

Immunogenicity analyses will be conducted for each of the 15 pneumococcal serotypes contained in V114 separately. To address the primary immunogenicity objective, evaluation of the serotype-specific IgG GMCs at 30 days postvaccination will include descriptive summaries and within-group 95% confidence intervals (CIs) to be calculated for each vaccination group. Point estimates for the IgG GMCs will be calculated by exponentiating the estimates of the mean of the natural log values. The within-group CIs will be derived by exponentiating the CIs of the mean of the natural log values based on the t-distribution.

A similar statistical approach will be used to evaluate serotype-specific OPA GMTs at 30 days postvaccination for each vaccination group. Point estimates of serotype-specific GMFR and its associated 95% CI will be calculated based on the t-distribution of natural log-transformed fold rise.

Reverse cumulative distribution curves for OPA titers and IgG concentrations will be graphically displayed by serotype at Day 30.

A detailed analysis strategy for immunogenicity endpoints is listed in [Table 1](#).

[figure not shown]
Table 1 Analysis Strategy for Immunogenicity Variables

Endpoint/Variable (Description, Time Point)	Primary vs. Supportive Approach [†]	Statistical Method	Analysis Population	Missing Data Approach
Primary Endpoint				
Anti-PnPs IgG GMCs at Day 30	P	Descriptive Statistics (estimate, 95% CI)	PP	Missing data will not be imputed
	S		FAS	
Secondary Endpoints				
Anti-PnPs OPA GMTs at Day 30	P	Descriptive Statistics (estimate, 95% CI)	PP	Missing data will not be imputed
GMFR from Day 1 to Day 30 for both OPA and IgG responses	P	Descriptive Statistics (estimate, 95% CI)	PP	Missing data will not be imputed

[†] P = primary approach; S = supportive approach.

CI = confidence interval; FAS = Full Analysis Set; GMC = Geometric Mean Concentration; GMFR = Geometric Mean Fold Rise; GMT = Geometric Mean Titer; IgG = immunoglobulin G; OPA = opsonophagocytic activity; PnPs = pneumococcal polysaccharide; PP = Per-Protocol.

The detectable ranges for OPA and IgG responses differ across serotypes. The limits of quantitation define the range of responses over which the assay provides precise and accurate measurements. [Table 2](#) gives the limits of quantitation defined for each serotype for OPA and IgG responses. For responses smaller than the lower limit of quantitation (LLOQ), half of the LLOQ is used for analysis when calculating the OPA GMTs and IgG GMCs. The value of the LLOQ is used for analysis when calculating the GMFR for OPA and IgG responses. For OPA and IgG responses that are larger than the upper limit of quantitation (ULOQ), a value equal to ULOQ + 1 is used for analysis.

3.6.2 Statistical Methods for Safety Analyses

Safety and tolerability will be assessed by clinical review of all relevant parameters including AEs and postvaccination temperature measurements.

The analysis strategy for safety parameters following each vaccination is summarized in [Table 3](#). The proportion of participants with solicited injection-site AEs (redness/erythema, swelling, tenderness/pain, and hard lump/induration Day 1 to Day 14 postvaccination) and solicited systemic AEs (muscle pain/myalgia, joint pain/arthralgia, headache, tiredness/fatigue, and hives or welts/urticaria from Day 1 to Day 14 postvaccination) will be provided along with the corresponding within-group 95% CIs (based on the exact binomial method proposed by Clopper and Pearson [[Collett, D. 1999](#)]). In addition, the broad AE categories consisting of the proportion of participants with any AE, a vaccine-related AE, an SAE, an AE which is both vaccine-related and serious, discontinuation due to an AE, and the proportion of participants who died will be summarized in the same manner. The proportion of participants with maximum temperature measurements meeting the Brighton Collaboration cut points (from Day 1 through Day 7) will also be provided along with the

corresponding within-group 95% CIs. Point estimates by vaccination group will be provided for all other safety parameters (specific AE terms and system organ class terms).

The analysis of safety parameters will be evaluated following administration of V114 or Prevnar 13™ (Day 30). Descriptive summaries of AEs following administration of V114 or Prevnar 13™ will include non-serious AEs within 14 days of vaccination and SAEs occurring Day 1 through completion of study participation (end of the study).

Table 3 Analysis Strategy for Safety Parameters

Safety Endpoint	95% CI for Within-Group Comparison	Descriptive Statistics
Injection-site redness/erythema (Days 1 to 14)†	X	X
Injection-site swelling (Days 1 to 14)†	X	X
Injection-site tenderness/pain (Days 1 to 14)†	X	X
Injection-site hard lump/induration (Days 1 to 14)	X	X
Muscle pain/myalgia (Days 1 to 14)†	X	X
Joint pain/arthritis (Days 1 to 14)†	X	X
Headache (Days 1 to 14)†	X	X
Tiredness/fatigue (Days 1 to 14)†	X	X
Hives or welts/urticaria (Days 1 to 14)	X	X
Any AE‡	X	X
Any vaccine-related AE‡	X	X
Any SAE‡	X	X
Any vaccine-related SAE‡	X	X
Discontinuation due to AE‡	X	X
Death‡	X	X
Maximum temperature measurements meeting the Brighton Collaboration cut points (Days 1 to 7)	X	X
Specific AEs by SOCs and PT		X

† Includes solicited events only.
‡ These endpoints are broad adverse event categories. For example, descriptive statistics for the safety endpoint of “Any AE” will provide the number and percentage of participants with at least 1 AE.
AE = adverse event; CI = confidence interval; PT = preferred term; SAE = serious adverse event; SOC = System Organ Class; X = results will be provided.

Safety analyses will be based on the observed data (ie, with no imputation of missing data).

Additionally, laboratory AEs will not be reported in summary tables as laboratory testing is not performed as part of the study and, as such, AEs would only be reported spontaneously. A listing of laboratory AEs will be provided.

A supportive analysis summarizing the proportion of participants reporting each of the solicited complaints on the VRC will be conducted in support of the primary safety analyses

that are based on solicited AEs. This supportive analysis will use the methodology specified in [Table 3](#) for solicited AEs. The analysis will be conducted on the subset of the APaT population who entered solicited complaints data on the VRC.

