7.3 Lost to Follow-up

If a participant fails to return to the clinic for a required study visit and/or if the site is unable to contact the participant, the following procedures are to be performed:

- The site must attempt to contact the participant and reschedule the missed visit. If the participant is contacted, the participant should be counseled on the importance of maintaining the protocol-specified visit schedule.
- The investigator or designee must make every effort to regain contact with the participant at each missed visit (eg, telephone calls and/or a certified letter to the participant's last known mailing address or locally equivalent methods). These contact attempts should be documented in the participant's medical record.
- Note: A participant is not considered lost to follow-up until the last scheduled visit for the individual participant. The missing data for the participant will be managed via the prespecified statistical data handling and analysis guidelines.

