8.1.8.1 Timing of Dose Administration

V114 or Prevnar 13™ will be administered as indicated in Section 1.3. All participants will be observed for 30 minutes postvaccination for any immediate reactions. This observation must be performed by blinded site personnel for all study vaccines (Section 1.3 and Section 6.3.3).

Participants must be afebrile for at least 72 hours prior to vaccination.

Blood samples must be collected and pregnancy tests (in WOCBP) must be administered before study vaccination.

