8.1.9 Electronic Vaccination Report Card

The eVRC was developed to be administered electronically via a hand-held device. This item was structured as recommended in the final Food and Drug Administration Patient Reported Outcome Guidance [U.S. Food and Drug Administration 2009]. The investigator or delegate will train the participant or participant's legally acceptable representative in the use of the eVRC as indicated in Section 1.3.

Body temperatures, injection-site reactions, vaccine-specific complaints, other complaints or illnesses, and concomitant medications or vaccinations will be recorded on the eVRC as described in Section 1.3 and Section 8.3.4. The investigator or delegate will review the data captured on the eVRC with the participant or participant's legally acceptable representative as indicated in Section 1.3.

For the AEs outlined above, the investigator will use the information provided by the participant or participant's legally acceptable representative both on the eVRC, and verbally at the time of eVRC review, to apply the appropriate assessment of intensity as described in Appendix 3.

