8.1.10 Telephone Contact Guide for Day 15 Postdose

Site personnel will contact study participants on Day 15 postdose to review eVRC data with the participant or participant's legally acceptable representative. The Day 15 Postdose Telephone Contact Guide will be provided by the Sponsor. This guide is designed to assist site personnel to collect any updates or edits to data previously entered on the eVRC from the participant or participant's legally acceptable representative. Any differences between eVRC data and the clinical database must be clearly explained in the participant's source documentation with an indication of where the information was obtained (eg, from the Day 15 Postdose Telephone Contact with the participant or participant's legally acceptable representative).

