9.5.2 Safety Analysis Populations

Safety analyses will be conducted in the All Participants as Treated (APaT) population, which consists of all randomized participants who received at least 1 dose of study vaccination. Participants will be included in the group corresponding to the study vaccination they actually received for the analysis of safety data using the APaT population. This will be the group to which they are randomized except for participants who take incorrect study vaccination; such participants will be included in the treatment group corresponding to the study vaccination actually received.

At least 1 temperature measurement obtained subsequent to study intervention is required for inclusion in the analyses of temperature.

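### Does the plan leave the denominator of the primary solicited-AE proportions open for a vaccinated child with no Day 1–14 information?

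*Combined protocol and SAP*

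**What the plan says.** The proportions of participants with solicited injection-site and solicited systemic AEs over Days 1–14 are primary endpoints (protocol section 3; supplemental SAP section 3.1). They are reported by group with exact (Clopper-Pearson) 95% intervals.

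Safety analyses are carried out in the APaT population, "which consists of all randomized participants who received at least 1 dose of study vaccination" (protocol section 9.5.2, repeated in supplemental SAP section 3.5.2). The missing-data rule for safety is one sentence in supplemental SAP section 3.6.2: "Safety analyses will be based on the observed data (ie, with no imputation of missing data".

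Three other analyses do carry a data requirement:

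- **Temperature** (protocol section 9.5.2): "At least 1 temperature measurement obtained subsequent to study intervention is required for inclusion in the analyses of temperature".
- **Full Analysis Set for immunogenicity** (supplemental SAP section 3.5.1): participants must "have at least 1 serology result at the time point for the analysis".
- **Supportive report-card analysis** (supplemental SAP section 3.6.2): limited to the part of APaT that entered solicited complaints on the card.

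For a participant lost to follow-up, protocol section 7.3 says: "The missing data for the participant will be managed via the prespecified statistical data handling and analysis guidelines".

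**The concern.** Take a child who is vaccinated, makes no entry on the electronic report card, misses the Day 15 call and does not come to Visit 2. APaT membership puts this child in the denominator with no event. The observed-data rule can be read the other way: the outcome was never observed, and counting the child as event-free resembles an imputation, which the same section rules out. No sentence names the denominator for this case. Section 7.3 points to guidelines set in advance, but for safety the guideline given is that single sentence.

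At stake is the denominator of a primary endpoint in two small groups. Keeping such children as non-events can only lower the proportion, and unequal numbers in the two groups could look like a difference between vaccines.

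**Working it through.** **Which reading the text supports**

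1. Both documents assign the safety analyses to APaT, and the entry conditions are randomization and a dose.
2. Where the authors want a data condition on a safety analysis, they write one. They do so for temperature and for the report-card analysis.
3. The report-card analysis is described as a subset of APaT and as support for the primary analysis. That contrast implies that the primary analysis is not cut down to such a subset.
4. The note to Table 3 of the supplemental SAP describes the broad AE summaries as the number and percentage of participants with at least one event. This counts reported events among those dosed and needs no value to be filled in.
5. The planning text (protocol section 9.9.2; supplemental SAP section 3.9.2) treats every randomized participant as evaluable for safety. This is not decisive, but it fits the same default.

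**How many children could be affected**

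The investigator works from what the family reports "both on the eVRC, and verbally at the time of eVRC review" (protocol section 8.1.9). The Day 15 call is a second source: "This guide is designed to assist site personnel to collect any updates or edits to data previously entered on the eVRC" (section 8.1.10). The card is reviewed again at Visit 2. Under section 8.1.12, Visit 2 activities are performed at withdrawal, and under section 7.3 missed visits are rescheduled. Immediate reactions are seen in everyone: "All participants will be observed for 30 minutes postvaccination for any immediate reactions" (section 8.1.8.1). Only a child missed by all later contacts is at issue.

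**The plan's own safety figures**

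- Chance of at least one SAE among 67 at 2.4%: 1 − 0.976^67 = 80.4% (plan: 80%).
- The same at 1 in 97: 1 − (96/97)^67 = 50.1% (plan: 50%).
- Upper limit with no SAE: 1 − 0.025^(1/67) = 5.36% (plan: below 5.4%).

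These reproduce. If 3 or 7 children were dropped from the V114 group, the zero-event limit would be 5.60% (n = 64) or 5.96% (n = 60).

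**Size of the denominator effect**

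Inputs: N = 67 and 33 from the plan. The number without information, m, and the event rate are assumptions, because the documents give neither. With x events, the two readings are x/N and x/(N − m), so x/N equals the rate among children with data times (1 − m/N). For example, 0.50 × (1 − 3/67) = 47.8%. Intervals are Clopper-Pearson.

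| Group | m | All APaT | Children with data | Shift (points) |
|---|---|---|---|---|
| V114 | 1 | 33/67 = 49.3% | 33/66 = 50.0% | 0.7 |
| V114 | 3 | 32/67 = 47.8% (35.4–60.3) | 32/64 = 50.0% (37.2–62.8) | 2.2 |
| V114 | 7 | 30/67 = 44.8% (32.6–57.4) | 30/60 = 50.0% (36.8–63.2) | 5.2 |
| V114 | 7 | 48/67 = 71.6% (59.3–82.0) | 48/60 = 80.0% (67.7–89.2) | 8.4 |
| Prevnar 13 | 1 | 16/33 = 48.5% | 16/32 = 50.0% | 1.5 |
| Prevnar 13 | 3 | 15/33 = 45.5% (28.1–63.6) | 15/30 = 50.0% (31.3–68.7) | 4.5 |

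With one to three children missing, the shift is small against intervals about 25 points wide (V114) or 36 points wide (Prevnar 13). Shifts above 5 points in the V114 group need about a tenth of it (7/67 = 10.4%) to have no information from any source. At an 80% rate that shift is not negligible: 80.0% lies just under the upper limit of 82.0% for 48/67.

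**The case for a change.** The strongest case for a change is that the default is inferred. The endpoint is primary, the plan writes data rules for neighbouring analyses, and the supplemental SAP even added words to tighten the Full Analysis Set. One sentence and one count row would settle the matter at almost no cost. The supportive report-card analysis does not fully replace them, because it leaves out children whose information came only verbally.

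It is true that the rule is unwritten, and that calling an unobserved child event-free is an assumption. It does not follow that the plan is unsound. The inference from the APaT definition and the two written exceptions is strong. A table of numbers and percentages shows its own denominator. Comparing the report-card N with the APaT N gives, for each group, an upper bound on the number of children without information.

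A more elaborate rule could do harm. If information counted only when collected inside the Day 15–19 and Day 30–44 windows, a child reviewed at withdrawal or at a rescheduled contact would be misclassified. If children without diary data were dropped unless an event had been recorded, inclusion would depend on the outcome and the rate would be biased upward.

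**Conclusion.** No change follows. This is a missing detail that analysts fill sensibly: the denominator is all APaT children, and the plan carried out that way gives a sound descriptive proportion with a visible N and a restricted-denominator analysis beside it. No stated figure or rule is shown to be wrong, and no hypothesis test depends on the choice.

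At a 50% rate the effect is 0.7 points (V114) or 1.5 points (Prevnar 13) for one child without information. It reaches 5.2 points, or 8.4 points at an 80% rate, only if 7 of 67 V114 children have nothing from the card, the calls or the visits. These counts and rates are assumptions. If the number proved large or clearly unequal between groups, it would deserve comment in the study report. A sponsor who wished to confirm the APaT denominator in a footnote could do so, but the analysis does not depend on it.
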